Probe based confocal laser endomicroscopy was first used in gastroenterology (endobrachy oesophagus, bilio-pancreatic lesions, colorectal polyps, inflammatory bowel disease...) (5). In pulmonary medicine pCLE came later to the light and is still an experimental technique but several studies are on going. Domains of interest are numerous:

- Pulmonary nodules evaluation;
- Interstitial lung diseases;
- Lung and bronchus infections;
- Lung rejection after transplantation (6);
- Lung emphysema (7);
- Mediastinal adenopathy (8);
- Pleural malignancies ;

Pleural effusion is a common finding in medical practice and often requires thoracocentesis and pleural biopsies to determine the underlying disease. However, thoracocentesis with pleural fluid cytology has limited sensitivity (up to 60% for repeated thoracocentesis) for a malignant pleural effusion diagnosis, one of the most common cause of pleural effusion (9-11). Therefore, thoracoscopy is often required, allowing direct pleural examination and biopsies with a sensitivity and a specificity of 94% and 100 % for malignant diseases(12,13). Nonetheless, this procedure is more invasive than a simple thoracocentesis. Recently, four studies demonstrated that pleural pCLE could be of value for the diagnosis of malignant pleural effusion. In 2018 Zirlik et al. showed that pCLE with fluoresceine performed in the pleural fluid after thoracocentesis was able to identify a malignant pleural effusion with 87 % sensitivity and 99% specificity compared

pleural fluid cytology (14). In 2019 Wijmans et al. showed that pCLE was able to guide pleural biopsies when the probe was passed through the biopsy needle during a thoracoscopy, an open thoracotomy or an ultra-sound or CT guided pleural biopsy when a malignant pleural mesothelioma was suspected(15). In 2021 our team published a prospective trial showing that pCLE during medial thoracoscopy was able to discriminate malignant from benign pleura(16,17). The same year, Sawada et al. showed that pCLE performed during surgery for lung cancer was able to identify a visceral pleural involvement with 100% sensitivity and 83% specificity(18). Considering these results and the low sensitivity of thoracocentesis for malignant pleural effusion identification, we conducted this proof of concept study to determine if mini-invasive close-blinded pleural pCLE performed through a Boutin's needle was feasible, safe and had a better sensitivity than thoracocentesis.

Study design

Exploratory study on a diagnostic procedure based on a cross-sectional study. We will prospectively include all patients referred to medical pleuroscopy for pleural effusion treatment or work-up.

The intervention was divided into four parts realized by the two same experienced investigators: First, the thoracocentesis for pleural fluid sampling and pathological examination; Second, the mini-invasive pleural pCLE (Alveoflex ®, lateral resolution 3 μ m, optical area 1.13 mm², depth of focus 0 - 50 μ m) (Cellvizio®, Maunakea technologies®, Paris, France); Third, the invasive pleural pCLE through the thoracoscope; Fourth, the traditional medical thoracoscopy with pleural examinations, biopsies and talc poudrage if required. Two different thoracoscopes were used during this study: A Wolf thoracoscope with an outer diameter of 7 mm (Richard Wolf GmbH, Knittlingen Germany ®) and a Storz single puncture thoracoscope with an outer diameter of 10 mm (Karl Storz GmbH, Tuttlingen, Germany ®). For pleural staining, 5ml of fluorescein 10% were intravenously administrated 5 min before pCLE acquisition. The investigators were aware of the clinical history of the patients during the intervention as it happens in real clinical practice.

For the mini-invasive pleural pCLE, the probe was blindly introduced in the pleural space through the Boutin's needle (traditionally used in medical thoracoscopy to induce a pneumothorax before insertion of the trocar) until satisfying images were recorded. At the same time, the two endoscopists rated 7 criteria (see the table 1 for the criteria and their interpretation). The part three (invasive pleural pCLE) started by the insertion of the trocar allowing to perform the medical thoracoscopy. For this part, the probe was gently applied on the parietal pleura through the working channel of the thoracoscope under vision control. If macroscopic abnormalities were noticed, pCLE was performed on the affected zones. In the absence of macroscopic abnormality, three random sites were selected. The same criteria were rated by the same two investigators. Finally, biopsies were systematically performed on the same sites for pathological diagnosis.

The assessed visual criteria were chosen in accordance with our previous publications and experience(16,17).

Methods

Inclusion/exclusion criteria

Every patient referred to medical thoracoscopy for pleural effusion willing to participate and signing informed consent.

Exclusion: unwilling to participate or unable to give informed consent; <18 years; pregnant woman; known allergy to fluorescein

Controls:

Pleural fluid cytological analysis

Aims:

To determine the feasibility and safety of mini invasive pleural pCLE assessment

To determine the sensitivity of mini invasive pleural pCLE compared to pleural fluid cytological analysis

Standard demographic, clinical, biological and endoscopic assessment

Gender, age

Medical background

Smoking habit

Current therapy

Blood: CRP, Albumin, total proteins, Hemoglobin, Platelet count, White blood cells, LDH

Pleural fluid: Cytological and bacteriological studies, LDH, Albumin, proteins

Sample size

No formal sample size calculation can be performed for such exploratory study. Every major patient referred for medical pleuroscopy will be proposed the study and screened if they give their informed consent.

Statistical analysis

The Fisher's exact test was used to analyze the link between pCLE qualitative variables and the final histological diagnosis. No adjustments are made for multiple variable testing.

2. Wang TD. Confocal microscopy from the bench to the bedside. *Gastrointestinal endoscopy*. 2005 Nov;62(5):696–7.

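### Does the blind pCLE step lack any way to fail, so that the feasibility aim cannot be assessed?

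*Combined protocol and SAP*

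**What the plan says.** The Aims section lists first: "To determine the feasibility and safety of mini invasive pleural pCLE assessment". The second aim is the sensitivity of the technique compared with pleural fluid cytology. The introduction calls the study a proof of concept and names feasibility first among its purposes.

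The Study design section sets out four consecutive parts: thoracocentesis, blind pCLE through the Boutin's needle, pCLE through the thoracoscope, and conventional thoracoscopy with biopsies. On the blind part it says that the probe was introduced "until satisfying images were recorded. At the same time, the two endoscopists rated 7 criteria", and on the rating it adds "see the table 1 for the criteria and their interpretation". That table is not in the text available for review. The next part is introduced by "The part three (invasive pleural pCLE) started by the insertion of the trocar", with no condition attached to the result of the blind part.

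On recruitment: "We will prospectively include all patients referred to medical pleuroscopy for pleural effusion treatment or work-up". The Statistical analysis section gives one method, saying that Fisher's "exact test was used to analyze the link between pCLE qualitative variables and the final histological diagnosis", and states that there is no multiplicity adjustment. The Sample size section says that no formal calculation can be made for an exploratory study.

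**The concern.** A feasibility study has to be able to record failure. Taken literally, the blind step continues until it works. What counts as a satisfactory image is not defined, no amount of effort is stated, and no abandoned attempt is described. A percentage produced on that basis would partly measure how long the operators persisted and what they were prepared to call adequate. Fisher's test of image criteria against histology does not yield a feasibility percentage, and no denominator is named for one.

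The second aim could also be affected. If malignant patients without usable blind images were left out, pCLE sensitivity would describe only those in whom the technique worked, while cytology would be judged in everyone. That would favour pCLE in the comparison the study was set up to make.

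**Working it through.** **Is there a figure to reproduce?** No. The documents state no sample size, feasibility rate, threshold or failure rate. The check is therefore a reading of the text, followed by illustrations on assumed inputs. The only input taken from the documents is the cytology sensitivity of up to 60% for repeated thoracocentesis, given in the introduction.

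**Step 1: can a failed attempt be observed?** The four parts run in sequence, and trocar insertion is not made to depend on the blind part. Patients come to the session because they were referred for thoracoscopy. A patient who reaches trocar insertion without usable blind images is therefore an identifiable failure. Nothing in the text says that such patients were impossible, withdrawn or excluded.

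**Step 2: is there a denominator?** The Study design section includes all referred patients, and the inclusion criteria require consent. All included patients is the natural denominator, though the text does not designate it as such.

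**Step 3: how much could effort matter?** Assume each probe placement succeeds independently with probability p. Success after k placements is 1 − (1 − p)^k.

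| p (assumed) | k = 1 | k = 3 | k = 5 | k = 10 |
|---|---|---|---|---|
| 30% | 30% | 66% | 83% | 97% |
| 50% | 50% | 88% | 97% | 99.9% |
| 30%, with 10% of patients never imageable (first row × 0.90) | 27% | 59% | 75% | 87% |

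For the last cell: 0.90 × (1 − 0.7^10) = 0.90 × 0.9718 = 0.8746.

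**Step 4: how much could the criterion matter?** Assume 40 attempts, with exact (Clopper-Pearson) 95% intervals.

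| Definition of success | Count (assumed) | Feasibility | 95% CI |
|---|---|---|---|
| some image obtained | 36/40 | 90.0% | 76.3 to 97.2 |
| malignant/benign call possible | 32/40 | 80.0% | 64.4 to 90.9 |
| all criteria ratable | 28/40 | 70.0% | 53.5 to 83.4 |

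Steps 3 and 4 show that more tries raise the rate and stricter definitions lower it. They carry no information about this trial, because every input is assumed.

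**Step 5: the comparison with cytology.** Let S be pCLE sensitivity among rated malignant patients, f the share of malignant patients with failed imaging, and C the cytology sensitivity. With failures counted as not detected, pCLE sensitivity is S × (1 − f). It equals C when f = 1 − C/S.

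| S (assumed) | f at C = 60% | f at C = 50% (assumed) |
|---|---|---|
| 70% | 1 − 0.60/0.70 = 14% | 1 − 0.50/0.70 = 29% |
| 80% | 1 − 0.60/0.80 = 25% | 1 − 0.50/0.80 = 37.5% |
| 95% | 1 − 0.60/0.95 = 37% | 1 − 0.50/0.95 = 47% |

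The introduction gives 60% as an upper figure for repeated taps, while the Study design section describes a single thoracocentesis step. The second column therefore shows a lower value. Below these failure shares the direction of the comparison stands. If failures were rated as negative, or if there were none, the reported sensitivity needs no correction at all.

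**The case for a change.** The strongest reply is that an exploratory label excuses a missing sample size but does not excuse leaving part of the first aim without an outcome definition. A descriptive feasibility result needs only a numerator, a denominator and an interval, and the text supplies none of them. It also leaves open whether the denominator is patients included, needles inserted or probes introduced.

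Much of this stands as a statement of fact. Success, failure handling and the feasibility proportion are not written down in the text available for review. Table 1 might define a non-evaluable category, but it is cited for the criteria and how to interpret them, so it cannot be assumed to settle image adequacy or stopping.

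Two supporting arguments are weak:

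- **Contrast with the thoracoscopic part.** There the plan says "In the absence of macroscopic abnormality, three random sites were selected". This fixes a number of sites, and only when nothing abnormal is seen. It sets no time, number of attempts or image standard per site, so it does not show that effort was specified in one part and neglected in the other.
- **Knowledge of clinical history.** The plan states "The investigators were aware of the clinical history of the patients during the intervention" and presents this as matching routine practice. History may sway a malignant/benign reading. No mechanism is apparent by which it would change whether an image is technically adequate.

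What the objection does not show is that a stated rule or number gives a wrong result.

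**Conclusion.** No change to the plan follows. The words about obtaining satisfactory images describe technique and are not a stopping rule or an endpoint. Failed attempts remain observable because the later parts do not depend on the blind part succeeding. What is missing is detail that an analyst would ordinarily fill by reporting interpretable acquisitions over attempts among all included patients, with an exact interval and an account of the failures. A simple proportion needs no prespecified test in an exploratory proof-of-concept study.

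The size of any effect cannot be obtained from the documents. For feasibility, the illustrations rest wholly on assumed inputs. For the comparison with cytology, harm requires that failures were dropped, which the text does not say. Even then, failures must reach 14% to 37% of malignant patients at a cytology sensitivity of 60%, or 29% to 47% at an assumed 50%, for pCLE sensitivity of 70% to 95% among those rated. Otherwise the direction is unaffected, and the effect may be zero.

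This conclusion assumes that failed attempts were noted in the procedure records and were not silently removed. The Study design text is largely in the past tense, so a definition of success written now might be post hoc, which limits what rewriting the plan could gain. A report that omitted failed attempts without saying so would be a fault in the report and would need to be raised there.

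### Does letting pCLE acquisition run until the images satisfy the operators, against one described fluid sample, spoil the sensitivity comparison?

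*Combined protocol and SAP*

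**What the plan says.** The Study design section sets out four parts. The comparator comes from part one: "First, the thoracocentesis for pleural fluid sampling and pathological examination". In part two the probe is passed blindly through the Boutin's needle "until satisfying images were recorded". The plan does not define a satisfying image, cap the acquisitions, ask for a count of them, or say how a failed one is handled. Rating happens during acquisition: "At the same time, the two endoscopists rated 7 criteria". The raters are not blinded to history: "The investigators were aware of the clinical history of the patients during the intervention as it happens in real clinical practice". Part three, pCLE through the thoracoscope, does have a site rule. Affected zones are examined if any are seen; otherwise, "In the absence of macroscopic abnormality, three random sites were selected".

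The Aims section states the comparison: "To determine the sensitivity of mini invasive pleural pCLE compared to pleural fluid cytological analysis". The introduction gives the purpose as finding out whether the technique "was feasible, safe and had a better sensitivity than thoracocentesis", and describes cytology in the literature as having "limited sensitivity (up to 60% for repeated thoracocentesis"). The Statistical analysis section names Fisher's exact test for pCLE variables against histology. It gives no method for pCLE against cytology.

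**The concern.** Two tests are compared under different acquisition rules. A poor pCLE view can be replaced on the spot, and nothing comparable is described for a poor fluid sample. The people who decide when to stop also score the criteria and know the history, so the stopping decision could depend on what the image shows. If it does, and one positive view makes the patient positive, every extra view is another chance to detect malignancy. Even a purely technical stop would remove failures from pCLE and leave them in cytology.

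The headline would be at stake. A finding that pCLE is more sensitive could reflect the number of looks and not the technique. The introduction itself treats repetition as relevant, since its cytology figure is for repeated thoracocentesis.

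**Working it through.** The documents give no sample size, expected pCLE sensitivity, number of views or failure rate, so there is no figure of the plan's own to reproduce. Everything below is illustration. The 60% is borrowed from the introduction as a convenient value, and all other inputs are assumptions.

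**1. Stop depends on image content, any positive view counts.** With single-view sensitivity m and k independent views, sensitivity is 1 − (1 − m)^k. For m = 0.60 and k = 3 this is 1 − 0.4³ = 0.936. With within-patient correlation ρ (beta-binomial):

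| ρ | pCLE, 3 views | gap over cytology at 60% |
|---|---|---|
| 0 | 0.936 | 34 points |
| 0.3 | 0.843 | 24 points |
| 0.6 | 0.742 | 14 points |
| 1 | 0.600 | 0 |

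The same mechanism costs specificity. An assumed 95% per view becomes 0.95³ = 0.857 with three independent views.

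**2. Same stop, different decision rule.** Suppose two of three independent views must be positive. Sensitivity is then 3m²(1 − m) + m³. For m = 0.60 this is 0.432 + 0.216 = 0.648, a gain of about 5 points. If the 60% came from two independent samples, the single-sample value is 1 − √0.4 = 0.368, and the majority rule turns 0.368 into 0.307, a loss of about 6 points. So the direction depends on the decision rule.

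**3. Stop depends on technical quality only.** Let both tests be 60% sensitive when adequate, and let cytology fail technically with probability t, counted as non-positive. If pCLE always succeeds in the end, the gap is 0.60 × t: 6, 12 or 18 points at t = 10%, 20% or 30%. If 10% of blind acquisitions never succeed and 2% of fluid samples are inadequate, pCLE is 0.60 × 0.90 = 0.540 and cytology 0.60 × 0.98 = 0.588. The gap is then 4.8 points in favour of cytology.

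**4. Chance of wrongly declaring pCLE better.** Take 30 malignant patients and a two-sided exact McNemar test at 5%. The plan names no paired test, so this one is only for illustration.

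| Scenario | Probability |
|---|---|
| Step 1, ρ = 0 / 0.3 / 0.6, cytology independent of patient detectability | 0.83 / 0.44 / 0.14 |
| Step 1, same ρ, detectability shared by both tests | 0.83 / 0.58 / 0.23 |
| Step 3, t = 10% / 20% / 30%, pCLE always succeeds, tests independent | 0.04 / 0.10 / 0.20 |
| One view each, equal tests | at most about 0.015 |

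The alarming values need a content-driven stop, several views, weak correlation and an any-positive rule, all at once.

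**5. What the text supports.** It does not say that several views were taken; one continuous acquisition also fits. It does not say that cytology is limited to one sample or that earlier cytology is excluded. The interpretation of the criteria is referred to table 1, which is not in the text available here. The more natural meaning of a satisfying image is technical quality, which points to step 3.

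**The case for a change.** The strongest case for a change runs as follows. The stop is open-ended, undefined and made by unblinded raters who score as they go. Part three shows that a site rule was practicable. Nothing planned would reveal whether an advantage came from extra looks. A definition of adequacy, a count of acquisitions and a first-sequence estimate would then seem a modest request.

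Part of this stands. The acquisition rule is loosely written, and a reader of the results would want to know how many acquisitions each patient had and how failures were counted. Those are reporting details, and a competent analyst would supply them.

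The first-sequence estimate is harder to defend. One view of a field of about 1 mm² is not the natural counterpart of one fluid sample, and repositioning a probe within a session is part of using it. If only satisfactory images were stored, the first stored sequence is already the satisfactory one and nothing is equalised. Re-reading it without the history would change two things at once, so any shift could not be put down to repetition. The text is largely in the past tense, and nothing says that rejected sequences were kept. Relabelling the comparison would alter no result. The 60% is background; the control is cytology within the study.

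**Conclusion.** No change to the plan is needed. The acquisition rules do differ, and under some assumptions that difference would favour pCLE, by up to 34 points in the extreme case. Under others it is nil or runs the other way, and the documents do not allow a choice between them. The aim is met by comparing what one pCLE session yields with what the study thoracocentesis yields, which is a fair question for a proof-of-concept study with no formal sample size. The undefined stopping word is a gap that can be filled sensibly when results are reported. Forcing equal attempts is a debatable trade-off with no assured gain. This rests on reading a satisfying image as a technically usable one. If the stop was in fact driven by malignant-looking features, the sensitivity advantage would need more caution and would have to be read beside specificity.

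### The plan does not say how blind pCLE attempts without satisfying images enter the sensitivity compared with cytology; leaving them out would make that comparison conditional on technical success

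*Combined protocol and SAP*

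**What the plan says.** The Study design section sets out four parts in sequence: thoracocentesis for cytology, mini-invasive pCLE, pCLE through the thoracoscope, and thoracoscopy with biopsies. For the second part, "the probe was blindly introduced in the pleural space through the Boutin's needle", and acquisition runs "until satisfying images were recorded. At the same time, the two endoscopists rated 7 criteria". The visible text does not define a satisfying image, does not describe a failed attempt, and gives no category for one. The criteria and their interpretation are in table 1, which is not in the text available.

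The Aims section lists two aims: "To determine the feasibility and safety of mini invasive pleural pCLE assessment" and "To determine the sensitivity of mini invasive pleural pCLE compared to pleural fluid cytological analysis". Neither has a stated denominator.

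The Statistical analysis section consists of one method, "The Fisher's exact test was used to analyze the link between pCLE qualitative variables and the final histological diagnosis", and a remark that multiplicity is not adjusted for. It gives no analysis set, no definition of sensitivity and no rule for non-evaluable pCLE. The Sample size section adds only that "No formal sample size calculation can be performed for such exploratory study".

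**The concern.** Feasibility is an aim because blind access may not always give usable images. The same failures bear on the second aim. A malignant patient in whom the blind probe gives no answer has not been diagnosed by it. From the point of view of someone choosing between this test and thoracocentesis, that is a miss.

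The acquisition wording describes only one end point, success, and rating takes place alongside it. The one planned analysis needs a rated variable for each patient. With no further rule, the natural result is a complete-case analysis of rated patients. Cytology, taken in part one, does not depend on whether part two succeeds.

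Reporting feasibility separately does not settle this, because the sensitivity figure itself would still describe only the patients in whom imaging worked. The background asks whether the blind approach is more sensitive than thoracocentesis, and the answer could depend on a denominator chosen after the results are known.

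**Working it through.** The documents state no sensitivity target, sample size or failure rate, so there is no figure to reproduce. What follows shows the direction of the effect and illustrates its size.

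**Direction.** Let N be the malignant patients in whom part two was attempted, F those without ratable images, and TP those rated as malignant by pCLE.

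- Over all attempts: TP / N.
- Among ratable attempts: TP / (N − F).

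Since N − F ≤ N, the second is never smaller than the first. With f = F / N, sensitivity over all attempts = (sensitivity among ratable attempts) × (1 − f). Here f is the failure rate among malignant patients, not among everyone enrolled.

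**Would restricting cytology to the same rated patients cure it?** Let C be the cytology detections among rated malignant patients and c those among the failures. The restricted difference is (TP − C) / (N − F); the difference over all attempts is (TP − C − c) / N. Whenever TP exceeds C, the restricted difference is at least as large. Pairing in rated patients therefore gives equal denominators but does not remove the conditioning.

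**Inputs for the illustration.**

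- Cytology 60%: the background describes "limited sensitivity (up to 60% for repeated thoracocentesis", so this is an upper figure for repeated sampling and not the value this study will observe.
- pCLE 87% among ratable attempts: borrowed from a cited study in which pCLE in pleural fluid "was able to identify a malignant pleural effusion with 87 % sensitivity and 99% specificity compared" with cytology. Technique and comparator differ from this study.
- pCLE 75% among ratable attempts: an assumption without a source in the documents.
- f: an assumption, shown as a range.

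| f | 75% × (1 − f) | 87% × (1 − f) |
|---|---|---|
| 5% | 71.3% | 82.7% |
| 10% | 67.5% | 78.3% |
| 20% | 60.0% | 69.6% |
| 30% | 52.5% | 60.9% |

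Parity with 60% is reached at f = 1 − 0.60 / (sensitivity among ratable attempts): 1 − 0.60 / 0.75 = 20%, and 1 − 0.60 / 0.87 = about 31%.

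In counts, with an assumed 30 malignant patients, 6 failures and 75% among the rest: 0.75 × 24 = 18 detected, so 18 / 24 = 75% among rated patients and 18 / 30 = 60% over all attempts.

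**The case against.** A reader might infer that the plan rates criteria only on satisfying images and drops the remaining patients. The documents do not support that. No sentence says that poor images go unrated, that failures are excluded, or that they count as negative. Enrolment covers all patients referred for pleuroscopy, and feasibility is an aim, so failures may well be recorded. Table 1 might contain a non-evaluable category. What stands against the plan is silence, not a stated exclusion.

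Nor do the documents say what follows a failed part two. If the images are merely poor, thoracoscopy and biopsy can proceed. If the needle did not reach the pleural space, the later steps might be affected and there could be no histology. It therefore cannot be assumed that every failed patient has a reference diagnosis.

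The planned Fisher's test is neither a sensitivity estimate nor a comparison with cytology, so strictly there is no stated denominator to be biased. That is correct, but it leaves the second aim with no rule at all, which is the gap at issue.

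A reader might also infer that the gain over cytology would vanish. That depends on the inputs: it happens at 20% failures with 75%, but not until about 31% with 87%, and later still if observed cytology is below 60%.

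Finally, counting failures as not detected is one convention; reporting the evaluable-only figure together with the failure rate is another. Both are informative, so both should be shown. The all-attempts figure should lead because the aim is to compare one diagnostic approach with another.

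**Conclusion.** The point holds as a gap in the plan. The visible text does not define a failed blind acquisition or say how one enters the sensitivity for the second aim. If failures are left out, as a complete-case analysis of rated variables would do, the comparison is conditional on technical success and can favour pCLE.

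The direction follows from the arithmetic. The size does not, because no failure rate is given. On the assumed values, a failure rate of 10% among malignant patients costs 7.5 points (75% to 67.5%) or 8.7 points (87% to 78.3%), and 20% costs twice as much. If no attempt in a malignant patient fails, the effect is nil.

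Confidence is medium, since table 1 is not visible and exclusion is an inference from the wording. In an exploratory, proof-of-concept study this is a change that should be made, not a flaw that invalidates the design.

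**What to change.** 1. Record every part-two attempt and whether ratable images were obtained, with ratable defined before the data are analysed. Distinguish failure to reach the pleural space from poor images.
2. For the second aim, take all patients with malignant final histology in whom part two was attempted. Count attempts without ratable images as not detected by pCLE, and non-diagnostic cytology as not detected by cytology. Compare the two tests in these same patients.
3. Report the number of attempted patients without final histology; they cannot enter either sensitivity.
4. Give sensitivity among patients with ratable images as a secondary figure, next to the failure rate.
5. If specificity is reported, do not count failures in benign patients as true negatives, since that would raise it without the test having given an answer.

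The cost is a definition, a short statement of the denominator, one recorded item per attempt and an extra line in the results table. The downside is a slightly lower headline pCLE sensitivity if any attempts fail.

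### The planned Fisher test cannot answer the accuracy aim: it estimates neither sensitivity nor specificity and leaves out cytology; the aim itself names sensitivity alone

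*Combined protocol and SAP*

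**What the plan says.** Under Aims, the second aim, and the only one about accuracy, is "To determine the sensitivity of mini invasive pleural pCLE compared to pleural fluid cytological analysis". The background text before Study design puts the question the same way: whether the mini-invasive technique "was feasible, safe and had a better sensitivity than thoracocentesis". Cytology of the pleural fluid is named as the control.

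Statistical analysis consists of two sentences. The first says that Fisher's "exact test was used to analyze the link between pCLE qualitative variables and the final histological diagnosis". The second says that multiple testing is not adjusted for. Nothing else is planned: no estimate of sensitivity or specificity, no confidence interval, and no comparison of pCLE with cytology. Specificity appears only in the background, for thoracoscopy (100%) and for two earlier pCLE studies (99% and 83%).

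Three features of Study design matter here. Enrolment is open: "We will prospectively include all patients referred to medical pleuroscopy for pleural effusion treatment or work-up". Ratings are made during the procedure: "At the same time, the two endoscopists rated 7 criteria". Biopsies are taken systematically after that. The reading of the criteria is given elsewhere ("see the table 1 for the criteria and their interpretation"), and that table is not in the text available for review.

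**The concern.** There are two problems, and the first is the firmer one.

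1. **Aim and analysis do not match.** The aim asks for a quantity (sensitivity) and a comparison (pCLE against cytology in the same patients). The analysis tests whether pCLE variables and histology are associated. Carried out exactly as written, it would leave the accuracy aim with no planned result, and any statement about sensitivity relative to cytology would rest on an unplanned analysis.

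2. **The aim covers half of accuracy.** A looser malignant call raises sensitivity and lowers specificity together. Sensitivity alone therefore cannot tell a better test from a looser one. If a comparison is added to answer the aim as worded, readers would not learn how many patients with benign histology the same call labels malignant. That number bears directly on whether a less invasive test is useful.

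**Working it through.** **Nothing to reproduce.** The plan gives no sample size, alpha or accuracy figure. Everything numerical below is illustration.

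**Step 1: what each part contains.**

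| | Accuracy aim | Planned analysis |
|---|---|---|
| Index test | mini-invasive pCLE | pCLE qualitative variables |
| Comparator | cytology | none |
| Reference | not named | final histology |
| Output | sensitivity, compared | p-values for association |

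The comparator and the output differ, so the analysis does not deliver the aim. This step needs no assumed number.

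**Step 2: the p-value does not identify accuracy.** Assume 20 malignant and 20 benign patients. Positive calls in 19/20 malignant and 10/20 benign (sensitivity 95%, specificity 50%) give two-sided Fisher p=0.0033. Positive calls in 10/20 malignant and 1/20 benign (sensitivity 50%, specificity 95%) give the same p=0.0033.

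**Step 3: what a sensitivity-only criterion permits.** Take a call that is positive in everyone: sensitivity 100%, specificity 0%. The background puts cytology at up to 60%. With 20 malignant patients assumed, cytology finds 0.60 × 20 = 12, so 8 pairs are discordant and all favour pCLE. Exact McNemar p = 2 × 0.5^8 = 0.008. This limiting case shows what the criterion allows; it does not predict how pCLE will perform.

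**Step 4: how far Fisher against histology protects.** Assumptions: m malignant and b benign patients, true sensitivity Se and specificity Sp, two-sided 0.05, and Fisher applied to one merged per-patient call. The chance of significance is

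P = Σx Σy Bin(x; m, Se) · Bin(y; b, 1−Sp) · 1[Fisher p(x, y) ≤ 0.05],

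with x and y the positive calls in malignant and benign patients. For Se = 90%:

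| Specificity | m/b = 20/10 | 30/20 | 40/30 |
|---|---|---|---|
| 10% | 0.013 | 0.018 | 0.027 |
| 30% | 0.226 | 0.380 | 0.526 |
| 40% | 0.421 | 0.656 | 0.828 |
| 60% | 0.804 | 0.964 | 0.996 |
| 83% | 0.989 | 1.000 | 1.000 |

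The test is discrete, so sizes near these can fall slightly lower: at 22/10 the formula gives 0.39 at specificity 40% and 0.78 at 60%. The 83% comes from a different setting, where pCLE at surgery could "identify a visceral pleural involvement with 100% sensitivity and 83% specificity", and serves only as the top grid point.

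Fisher thus usually stops a near-uninformative call. It often passes a call with specificity 40%, and it barely separates 60% from 83%.

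**Step 5: one concrete data set.** Positive calls in 27/30 malignant and 12/20 benign patients:
- Fisher p=0.017
- sensitivity 27/30 = 90%
- specificity 8/20 = 40%, Clopper-Pearson 95% CI 19.1% to 63.9%

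With 16/20 false positives instead, Fisher p=0.42.

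**The case against.** The case for leaving the plan alone has real content.

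- **It is an exploratory proof of concept**, with feasibility and safety listed first and low cytology sensitivity as the stated problem. That explains the missing sample size and the emphasis on sensitivity, and it tempers the severity. It does not explain why the sensitivity named in the aim is never estimated. Estimates with intervals are what an exploratory accuracy study can deliver.
- **The counts would exist.** Fisher against histology uses benign as well as malignant patients, so each table holds that criterion's sensitivity and specificity. This stands in part: no data are lost. But with seven criteria and two raters, per-criterion tables are not a per-patient call, and none of them contains cytology.
- **The illustration is not the planned analysis.** This is correct. It merges the criteria into one call and assumes the patient numbers and accuracies. It supports the general point that a significant p-value does not fix specificity, and it does not measure this trial's risk.

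A reader might infer more than the documents support:

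- *That the plan would declare pCLE more sensitive despite poor specificity.* The written analysis cannot yield that conclusion, because cytology is not in it. It would take a further comparison that nobody has written down.
- *That the malignant call is lenient.* The table that interprets the criteria is not available, so nothing can be said about how strict the rule is.
- *That a rule was chosen with histology in hand.* The past tense ("we conducted this proof of concept study to determine if mini-invasive close-blinded pleural pCLE") means that histology may already be known. It does not show that it influenced anything.

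**Conclusion.** The concern holds as a mismatch between aim and analysis, and it should be corrected before accuracy results are reported. This conclusion rests only on the wording of Aims and Statistical analysis. The second part, that sensitivity alone is an incomplete aim, follows from how the two measures move together and needs no assumed figure.

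The size of the residual gap does depend on assumptions: 20 to 40 malignant and 10 to 30 benign patients, true sensitivity 90%, and one merged call. On these, the chance of a significant Fisher result is about 0.4 to 0.83 at specificity 40%, about 0.8 to 0.996 at 60%, and about 0.99 to 1.00 at 83%. Significance is therefore only a partial safeguard. Because the design already collects what is needed, this is a gap in planned estimation and reporting. It is not a flaw in enrolment or verification.

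**What to change.** **Main change.** Restate the accuracy aim as the sensitivity and specificity of one per-patient mini-invasive pCLE call. Report both against final histology with exact 95% CIs, beside cytology from the same session. Lay the results out as two paired 2×2 tables (pCLE positive or negative by cytology positive or negative), one for patients with malignant histology and one for those with benign histology. Word the conclusion as sensitivity at the observed specificity. The Fisher tests of individual criteria can stay as supporting description.

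**Secondary.** Define the call by the interpretation in Table 1, using the ratings recorded before biopsy. If Table 1 has no rule for combining the two raters, state one. If histology is already known when that rule is written, label it post hoc.

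**Cost.** A little more analysis, no new patients or procedures, and possibly a less favourable headline. The specificity interval will be wide if few benign patients enrol. At an observed 90% it runs from 55.5% to 99.7% with 9/10, 68.3% to 98.8% with 18/20, and 73.5% to 97.9% with 27/30. That width is real uncertainty which a sensitivity-only report would leave unseen.
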